**9B. Sample Size.**

**9Bi.** Provide an estimated sample size for the lifetime of the study at this investigator's sites.

100 to 400

**9Bii.** Describe the basis for that estimate.

We plan to screen as many as participants as possible that would allow us to enroll a minimum of 100 participants in a two-arm randomized controlled trial. Each arm will require a minimum of 50 participants. We determined this sample size in a few ways. One, the typical sample size for a between-subjects study comparing non-deceptive placebos to a control group ranges from 30 to 50 per condition (Kaptchuk et al., 2010; El Brihi et al., 2019; Locher et al., 2017). Two, from a more practical standpoint, we only have the financial resources to run approximately 50 in each condition. We are applying for additional funding, but for now, we only have a budget for 50 in each condition. Three, we determined 50 participants in each arm by hypothesizing a d effect size of .60 between the control group and each of the treatment arms with a power of .80 at an alpha level of .05. Non-deceptive placebo studies have typically used an ANOVA model followed up by pairwise comparisons. These effect sizes are calculated from these pairwise comparisons.

Our assumption of a d effect size of .60 is a liberal assumption based on the literature in which the d effect size between a non-deceptive placebo and a no treatment control ranges from .30 to 1.00. The most relevant non-deceptive placebo study is El Brihi et al. (2019) in which they tested the effects of non-deceptive placebos on emotional distress and positive mental well-being. Comparing two types of non-deceptive placebos versus a control showed a non-deceptive placebo effect that ranges from a Cohen's d of .78 to 1.01 on emotional distress. Comparing two types of non-deceptive placebos versus a control showed a non-deceptive placebo effect that ranges from a Cohen's d of .55 to .93 for psychological well-being. As such, we estimate that a d effect size of .60 between a control group and our non-deceptive placebo group because our primary outcomes is also emotional distress and psychological well-being. A .60 d effect size is within a reasonable range of what is expected regarding a non-deceptive placebo effect on emotional distress. This will allow us to run approximately 50 in each condition, which is more than the sample size of the El Brihi et al. (2019) study in which they had n = 29 in the control condition and n = 30 and n = 31 in each of the non-deceptive placebo condition.

For our primary outcomes, we plan to run a 2 (Group) by 3 (Time: Time 2, Time 3) mixed factorial ANOVA (while controlling for baseline levels) followed by independent pairwise comparisons at each of time point. When possible, we plan to use multiple imputation methods to account for missing data. If a participant is missing data from 2 or more time points for our primary outcome, they will be removed for analyses. If a person is unresponsive for 5 days, we will consider them a dropout. We will send a final letter indicating that we apologize for their drop

and that they can contact us if they need anything and provide them resources if they require it. If participants wants to drop out, we can inquire why and offer them resources and contact information for future studies.

Again, we also only have a budget to run 50 participants in each condition. We plan to apply for further funding but for now, this is our limit. We want the option to test more than 50 in each condition because it will increase our confidence in any effect we find. If we receive funding, we will run more than 50 in each condition, but we will not enroll more than 200 participants in each arm. The 200 in each arm maximum will allow us to detect a d effect size of .30 with some room for error such as participants dropping out or not filling out all of our measures.

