Clinical Trial Statistical Analysis Plan

Title: Effects of Open-label Placebos Administered Through Telehealth on COVID-related Stress, Anxiety, and Depression

Brief Title: Effects of Open-label Placebos on COVID-related Psychological Health

Study Sponsor: Michigan State University

Principle Investigator:

Name: [name]

Official Title: Professor of Psychology

Affiliation: Michigan State University

[contact]

Email: [contact]

NCT Number: NCT05035550

Version Date: 1.22.21

Statistical Analysis Plan

All analyses were conducted on SPSS version 26 (IBM, Armonk, NY). Prior to our primary analyses, we first interpolated missing data using a maximum likelihood estimation (MLE). Second, we conducted an independent sample t-test on baseline measures of each primary outcome measure to ensure that the control and open-label placebo group did not differ prior to the administration of the intervention.

The primary outcomes at the endpoint (reduction in COVID stress, perceived stress, anxiety, and depression) were calculated using change from baseline scores (endpoint minus baseline) with positive numbers indicating greater reduction in symptoms at endpoint. First, each primary outcome was submitted to a one-way analysis of covariance (ANCOVA), with group as the independent variable and the mean baseline score for each outcome measure submitted as a covariate to control for variability in baseline scores (Lembo et al., 2021; Van Breukelen, 2006). We reported outlier detection procedures and additional robust analyses in the Supplementary Materials. Effect sizes for pairwise comparisons were calculated using Cohen's d. Secondary outcomes were analyzed using descriptive statistics and t-tests. All significance tests were analyzed at $p = .05$.

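### The protocol and SAP specify different missing-data methods, and if the SAP's is a single fill-in analysed as observed, either the error rate or the effect estimate is wrong

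*Protocol*

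**What the plan says.** **Method.** Protocol section 9Bii states: "When possible, we plan to use multiple imputation methods to account for missing data". The SAP states: "Prior to our primary analyses, we first interpolated missing data using a maximum likelihood estimation (MLE"; after that, "each primary outcome was submitted to a one-way analysis of covariance (ANCOVA". The SAP does not say whether values are filled in once or several times, which variables inform them, or how uncertainty about them reaches the standard error.

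**Who is analysed.** Section 9Bii gives a rule: "If a participant is missing data from 2 or more time points for our primary outcome, they will be removed for analyses". The SAP has no removal rule and names no analysis set.

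**Time points.** Section 9Bii describes the primary model as "a 2 (Group) by 3 (Time: Time 2, Time 3) mixed factorial ANOVA", which announces three levels and lists two. Section 15 describes four surveys, the first two serving as baseline. It requires the First, Second and Fourth and allows only the Third to be missed.

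**People who leave.** Section 9Bii says "If a person is unresponsive for 5 days, we will consider them a dropout", followed by "We will send a final letter indicating that we apologize for their drop" and an offer of resources. Section 16A ends participation for those under significant stress who want another treatment and for anyone who no longer wishes to continue. No section says that the last survey is still sought from these people. Loss is foreseen: the ceiling of 200 per arm is justified "with some room for error such as participants dropping out or not filling out all of our measures".

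**The concern.** Multiple imputation and a single fill-in are different analyses of the same primary outcomes. Multiple imputation adds the uncertainty about the missing values to the standard error. A single fill-in followed by an ordinary ANCOVA does not, because the software counts invented values as observations. At stake is whether the p-value, or the size of the estimated effect, can be taken at face value.

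There are two lesser issues. The removal rule cannot be counted with certainty while time points and surveys do not match. In addition, people may leave for reasons tied to stress, which is what the primary outcomes measure. If that happens unequally between arms, the comparison is biased.

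**Working it through.** **1. The plan's own figures.** The documents give no expected loss rate, so there is no missing-data figure to reproduce. The nearest is 50 per arm for d = 0.60, power .80, alpha .05. A two-sided t-test needs 45 per arm, and 45/(1 − 0.10) = 50, so the figure would absorb 10% loss, although the protocol does not say this is its basis. For d = 0.30 the need is 176, and 1 − 176/200 = 12%. Loss of 10% and 20% is used below as an assumed range.

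**2. The passages side by side** (taking the First and Second Surveys as baseline and the Fourth as endpoint):

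| Missing | Protocol 9Bii | Protocol 15 | SAP |
|---|---|---|---|
| Third only | kept, imputed | allowed | filled in |
| Fourth only | kept, imputed | not allowed; consequence for analysis unstated | filled in |
| Third and Fourth | removed, if each counts as a time point | not allowed | no rule stated |

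**3. Single fill-in with arm and baseline in the model.** Let f be the fraction missing at random in each arm. Filled values lie on the fitted surface, so the ANCOVA estimate equals the complete-case estimate. The residual variance is spread over n people instead of n(1 − f), and the design also counts n. Each step multiplies the variance by about (1 − f), so the reported standard error is about (1 − f) times the true one.

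Type I error = 2[1 − Φ(1.96(1 − f))]

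- f = 10%: 2[1 − Φ(1.764)] = 7.8%
- f = 20%: 2[1 − Φ(1.568)] = 11.7%

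Simulations (50 per arm, no true effect, correlation .5, 6,000 to 8,000 runs) agree: 7.3% to 8.3% at 10% missing and 11.7% to 12.3% at 20%. Adding the Third Survey to the fill-in gives 7.1% and 10.0%. Adding random noise to a single fill-in gives 7.0% and 10.8%.

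**4. Single fill-in with arm left out.** Filled-in people carry no arm difference of their own, so the estimate shrinks by (1 − f): 0.60 × 0.90 = 0.54 and 0.60 × 0.80 = 0.48. The standard error shrinks in nearly the same proportion, so type I error stays at about 5% (4.7% to 5.2% simulated). The test survives, but the effect size is too small.

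**5. The alternatives, same random loss.** Removal gives type I error of 4.7% to 5.4%. Multiple imputation with 20 imputations and pooled standard errors gives 5.0% to 5.3%. Neither shrinks the effect.

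**6. People missing both follow-ups.** Only arm and baseline remain to impute from. By step 3 the filled-in estimate equals the removal estimate, so the two rules give nearly the same answer once the standard error is handled properly.

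**7. Outcome-related loss.** Suppose loss follows an index correlated .5 with endpoint stress. Among those who stay, the index mean moves by φ(z)/(1 − f), where z is the cut-off: 0.350 at f = 20% and 0.195 at f = 10%. After baseline adjustment the bias is about (0.350 − 0.195) × .5 × (1 − .5²) = 0.058 SD. Simulation at 50 per arm gives 0.061 to 0.065 SD (type I error about 7%) for 20% versus 10%, the same size in the other direction when the rates are swapped, and about 0 for equal loss by the same mechanism. Varying the index correlation from .1 to .7 (run at 500 per arm) gives 0.01 to 0.09 SD.

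**8. What extra data would buy.** For people missing only the Fourth Survey, at 20% versus 10% and an assumed Third-Fourth correlation of .7, using the Third cuts the bias from 0.04 to 0.00 SD if loss follows Third-Survey stress, and from 0.05 to 0.03 SD if it follows the endpoint. Recovering half the lost endpoints (500 per arm) cuts 0.056 SD to 0.027 if a random half returns. If the most stressed half stay lost, there is no gain (0.061).

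**The case against.** The SAP is one page, and its sentence on maximum likelihood does not say that values were filled in once. The inflated error rate needs two facts it omits: a single fill-in, and arm in the fill-in model. This stands. A reader might infer that the disagreement on method in itself raises the false-positive rate. The documents do not support that, since with arm left out the rate is nominal and the fault is a diluted effect. What remains is that each single fill-in examined has a cost and that the SAP rules none of them out.

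A reader might also infer that the SAP contradicts the protocol by analysing people who miss both follow-ups. It never says so, and the protocol's rule may have been applied first. This is silence against an explicit rule, and step 6 shows it has little effect.

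Section 15 can be read either as a condition of participation or as an exclusion from analysis. It does not settle which, so it cannot be cited as a firm third analysis rule.

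Finally, bias from unequal loss is conjecture about rates the documents do not give. Daily pills in one arm and assessment only in the other make unequal loss plausible, but neither its size nor its direction can be known in advance. Seeking the last survey from people already silent may also achieve little.

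**Conclusion.** The two documents name different missing-data methods for the primary analysis, and this should be fixed. If the SAP's step is a single fill-in analysed as observed, type I error is about 8% and 12% (arm included), or a true 0.60 SD becomes about 0.54 and 0.48 (arm left out), at 10% and 20% missing. These figures assume 50 per arm, a correlation of .5 and random loss. The disagreement in wording is certain; the figures depend on a fill-in step that the SAP does not describe.

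The missing analysis set is a minor point. Bias from outcome-related loss is possible but unquantified: about 0.06 SD at an assumed 20% versus 10%, one tenth of the planned effect, and about 0 if loss is equal in rate and mechanism. Nothing here shows that the trial's result is invalid.

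**What to change.** 1. Replace the SAP's fill-in with one method: multiple imputation with pooled standard errors, or a likelihood-based repeated-measures model. Either should include arm, baseline and every available survey, including the Third. Align section 9Bii with it.
2. State one primary analysis set, all randomised participants as assigned, and keep the removal rule in section 9Bii as a sensitivity analysis. Map the four surveys to named time points so that the rule can be counted.
3. Reconcile sections 9Bii, 15 and 16A on whether leaving also ends data collection. Where consent is not withdrawn, offer the Fourth Survey to everyone who leaves, including those whose participation ends under section 16A. The termination conditions stay as written. Section 18A says surveys are administered through Zoom, so each recovery may need staff time, and the gain may be small.
4. Report loss by arm and reason.

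The cost is revised wording, a little more analysis work, some extra contacts, and slightly wider standard errors than a single fill-in would show. The SAP is written in the past tense; if data collection has ended, the recovery offer in item 3 comes too late, but the analysis and reporting changes can still be made.

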**10. Benefits.**

Describe any potential direct benefit(s) to subjects in this study, if any and the importance of the knowledge that may reasonably be expected to result. Within the description, do not include payment to subjects as a benefit.

The intervention group will develop a better understanding of placebos and placebo effects. There is a possibility that this understanding may lead those in the intervention group to feel less stress and anxiety related to COVID-19 compared to the control group. In terms of societal benefits, there is a possibility that we may provide support for a cost-effective and scalable intervention to help people manage their stress and anxiety related to COVID-19.

**11. Screening, Recruitment, and Determining Eligibility.**

**11A. Describe how subjects will be identified and recruited, including who will perform the recruitment.**

Broadly, our target sample is any Michigan resident that fits our eligibility criteria. Participants will be between 18 and 30, English as their primary language, do not have a self-reported history of severe mental illness, do not have a current diagnosis of COVID-19, no major health problems such as heart and lung diseases, and is able and willing to participate in a longitudinal study spanning 17 to 20 days. In order to ensure people's identity, people will be required to show their ID in a HIPPA compliant Zoom call. In order to ensure that our sample is currently experiencing a moderate amount of stress and anxiety related to COVID-19, we will also only enroll participants who score a 35 or higher on the COVID Stress Scale.

For those in the intervention condition, we will have additional criteria asking if they would be willing to provide an address where we can send them a bottle of placebo pills and if they are willing to take placebo pills 2 weeks. People in the intervention group will also indicate that they are willing to take pills for 2 weeks and not be allergic to common ingredients found in pills such as microcrystalline cellulose, silica, gelatin, titanium dioxide, Red # 3, and Blue #1.

Participants will be recruited from the MSU student population and broader Michigan community. Since the study is online, we are not restricted by East Lansing geography. We plan to recruit online through Craigslist, Facebook, and other research online platforms such as ResearchMatch.

We will also recruit through the Paid Subject Pool from the Communication Arts and Sciences Department that is managed by [name].

We are also partnering with a collaborator from University of Michigan to help with recruitment, and we plan to use their health research participant pool. The collaborator will not interact or intervene with subjects for research purposes, they will not collect data or obtain consent or study or analyze any of the data with identifiable information. The University of Michigan IRB will

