**4. Reasonably Foreseeable Risks.**

**4A.** There are (select one of the following):

- No reasonably foreseeable risks to subjects
- Reasonably foreseeable risks to subjects

**4B.** Explain the selection. *If you selected that there are reasonably foreseeable risks to subjects, describe the risks, considering physical, psychological, social, legal and economic risks.*

We expect the risk to subjects to be minimal. There is a small risk of psychological distress from replying to questions regarding their psychological and physical health within the COVID-19 pandemic context. Participants in the intervention conditions who are not accustomed to taking pills may also experience distress from taking inactive placebo pills

**4C.** If you selected that there are reasonably foreseeable risks, describe the procedures for protecting against or minimizing potential risks and provide an assessment of their likely effectiveness.

In order to protect subjects from the risk of psychological distress from replying to questions regarding their psychological and physical health within the COVID-19 pandemic context, participants will have the option to skip any questions or withdraw from the study at anytime. Participants in the intervention conditions will be asked if they are willing to take placebo pills, and those who are not comfortable or wishes not to do so will not be able asked to participate in the study. Moreover, participants will receive resources, which can provide additional support and counseling if needed.

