Despite their efficacy, non-deceptive placebo studies are typically done in person to help facilitate beneficial effects. Moreover, placebo research suggests that an in-person interaction with an authority figure in the form of a medical doctor or experimenter may be an important ingredient in order to maximize placebo effects (Kaptchuk et al., 2008). Nevertheless, positive expectations and beliefs in the efficacy of treatment are powerful ingredients of placebos that can be leveraged online, as research indicates that expectations and beliefs can be effectively changed remotely and thus lead to the intended beneficial effects (Geers et al., 2019; Kaptchuk et al., 2010; Yeager et al., 2019).

In this project, we will test the efficacy of a cost-effective and scalable telehealth interventions. Participants will be randomly assigned to one of two conditions: 1) a no-treatment,

assessment only control (NT Control) and 2) a non-deceptive placebo intervention administered through an informational video and remote interaction with an experimenter (NDP Video + Experimenter). The informational video will consist of a brief explanation of placebos and the placebo effect, how placebos provide beneficial effects for many different conditions, how placebos can affect behavior and biology, and how placebos can still work even when people know they are taking one. In the NDP Video + Experimenter intervention, participants will remotely interact with an experimenter who will reiterate and emphasize the placebo information and provide instructions on how to take the open-label placebo pills. Participants in the NDP Video + Experimenter intervention will be instructed to take open-label placebo pills on a daily basis for two weeks.

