### 12. Consent Process.

**12A.** If the study involves adults, consent will be obtained from (select appropriate option(s)):  Not Applicable

All subjects  
 Some subjects  
 No subjects (consent will not be obtained)

***CLICK IRB: Upload the consent document, script, etc. (including translations) to the Consent Forms and Recruitment Materials SmartForm page, Question 1.***

**12B.** If the study involves children, parental permission will be obtained from (select appropriate option(s)):  Not Applicable

Both parents or guardians (unless one parent is deceased, unknown, incompetent, or not reasonably available, or when only one parent has legal responsibility for the care and custody of the child)  
 One parent or guardian  
 Will not be obtained

*CLICK IRB: Upload the parental permission forms to the Consent Forms and Recruitment Materials SmartForm page, Question 1.*

**12C.** If the study involves children, child assent will be obtained from (select appropriate option):  Not Applicable

- All children
- Some children
- Will not be obtained

*CLICK IRB: Upload the child assent form to the Consent Forms and Recruitment Materials SmartForm page, Question 1.*

**12D.** Describe the consent process, including an explanation of your selection(s) above. If the study involves screening activities, please describe whether consent will be obtained and if consent will not be obtained, explain how the screening data will be used. If only some subjects will provide consent, explain who will or will not provide consent. If only some children will provide assent, explain which children will and will not provide assent.

The consent process will happen two times. First, consent will be obtained before the prescreening questionnaire is administered. The prescreening questions will be administered via an online survey through the Qualtrics platform. Once potential participants complete the survey, trained research assistants and personnel will determine if participants are eligible to be part of the study. Those who are not eligible will be sent an email thanking them for their participation. Those who are eligible will be contacted in order to set up a meeting for a potential enrollment.

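### Willingness to take placebo pills is written as an entry criterion for the intervention arm only, and the time of randomisation is not given, so the two arms may be selected by different rules.

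*Protocol*

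**What the plan says.** Protocol section 11A begins with criteria for all participants: age, language, health history, COVID-19 status, availability and a minimum COVID Stress Scale score. It then changes scope: "For those in the intervention condition, we will have additional criteria asking if they would be willing to provide an address", and willingness to take placebo pills for two weeks. The next sentence repeats the restriction: "People in the intervention group will also indicate that they are willing to take pills for 2 weeks and not be allergic to common ingredients".

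Section 4C (risk minimisation) says the same: "Participants in the intervention conditions will be asked if they are willing to take placebo pills". Its following clause is garbled, but the sense is that people who are unwilling do not take part. No matching rule is given for controls.

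On allocation, section 9A says "Participants will be randomly assigned to one of two conditions" and gives no time point. Section 12D describes an online prescreen under a first consent, after which "trained research assistants and personnel will determine if participants are eligible to be part of the study". Eligible people are then contacted about enrolment and go through a second consent. Randomisation is not placed anywhere in that sequence.

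On who is analysed, section 9Bii states "If a participant is missing data from 2 or more time points for our primary outcome, they will be removed for analyses", and section 15 stops people who miss required surveys. The SAP names no analysis set. Its provisions for baseline comparability are an "independent sample t-test on baseline measures of each primary outcome measure to ensure that the control and open-label placebo group did not differ" and an ANCOVA "with group as the independent variable and the mean baseline score for each outcome measure submitted as a covariate".

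**The concern.** A criterion limited to one arm can be applied as written only once the arm is known. The text therefore permits people to be excluded after assignment, from the intervention arm alone.

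Of the three arm-specific items, pill willingness matters most. Someone who declines a pill they know to be inert plausibly expects less from placebos, and section 9A itself treats expectation and belief as central to how placebos work. The outcomes are self-reported, the intervention is unblinded and the comparator is no treatment. If refusers leave one arm only, the arms are no longer exchangeable on a characteristic that may affect the outcome, and the primary comparison mixes selection with treatment effect. A mailing address and an excipient allergy are less likely to be related to outcome.

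No stated rule closes the gap. The plan does not say that everyone is analysed as randomised. The baseline test has little power against a shift of the size in question, and the covariate removes only the part of the difference that the baseline score carries.

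**Working it through.** **Step 1: the text side by side.**

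| Question | Where it would be answered | What is found |
|---|---|---|
| Who must be willing to take pills? | Protocol 11A, 4C | Intervention participants only |
| Who must give an address and be free of excipient allergy? | Protocol 11A | Intervention participants only |
| Are these among the items screened for everyone? | Protocol 11B1 | Not listed, but the list is given as examples and is not exhaustive |
| When does randomisation occur? | Protocol 9A, 12D | Not stated |
| Are all randomised people analysed as randomised? | Protocol 9Bii, SAP | Not stated |

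**Step 2: bias under stated assumptions.** The plan has no figure to reproduce, and it gives neither input, so both are assumed:

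- p: share of the assigned intervention arm removed.
- δ: gap in endpoint between removed and kept people, in SD, remaining after baseline adjustment.

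Suppose there is no treatment effect and the kept group has mean μ. The intervention arm then has mean μ. The control arm still holds both kinds of people, so its mean is (1 − p)μ + p(μ + δ) = μ + pδ. Hence bias = p × δ.

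**Step 3: false-positive rate.** This uses a two-sided t-test at 0.05 with n per arm, 2n − 2 degrees of freedom, SD 1 in both arms, each arm filled to n, and noncentrality = bias × √(n/2). For n, 50 is the planned minimum and 200 the maximum per arm in section 9Bii. √(50/2) = 5 and √(200/2) = 10.

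| p | δ | Bias (SD) | Share of d = 0.60 | Share of d = 0.30 | Noncentrality, n = 50 / 200 | Rejection, n = 50 | Rejection, n = 200 |
|---|---|---|---|---|---|---|---|
| 5% | 0.25 | 0.0125 | 2% | 4% | 0.0625 / 0.125 | 5.0% | 5.2% |
| 10% | 0.5 | 0.05 | 8% | 17% | 0.25 / 0.5 | 5.7% | 7.9% |
| 20% | 0.5 | 0.10 | 17% | 33% | 0.5 / 1.0 | 7.9% | 17.0% |
| 20% | 1.0 | 0.20 | 33% | 67% | 1.0 / 2.0 | 16.8% | 51.4% |

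The effects 0.60 and 0.30 are those named in section 9Bii for 50 and 200 per arm. Over p = 5% to 30% and δ = 0.25 to 1.0, the bias runs from 0.0125 to 0.30 SD.

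A simulation in which the control arm really is a mixture, with SD 1 within each kind of person, gives slightly lower rates for the last three rows: 5.7%, 7.8% and 15.8% at 50 per arm; 7.8%, 16.5% and 49.0% at 200. The mixture widens the control arm's spread a little.

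**Step 4: would the baseline t-test reveal it?** Suppose refusers also differ at baseline by 0.5 to 1.0 SD and p = 20%. The baseline means then differ by 0.10 to 0.20 SD, and by the same calculation the test at 50 per arm is significant only 7.9% to 16.8% of the time.

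**Step 5: the benign case.** If everyone is asked before assignment, p = 0 and the bias is 0.

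**The case against.** The strongest reply is that the questions may well have been put to everyone before assignment. The items are called criteria and stand under a heading on screening and eligibility. Section 4C speaks of the unwilling not entering the study, not of leaving an arm. Section 12D has staff decide eligibility from the prescreen, before the enrolment meeting, and says nothing about arms. The arm-specific phrasing could also be left over from a design with several intervention arms: section 4C uses a plural for the intervention conditions, and section 9Bii refers to more than one treatment arm. The prescreen questionnaire and consent pages are not available here and might settle the order.

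All of that is possible, and it is why actual bias is not claimed. It does not remove the gap: the criteria are twice restricted to the intervention arm, and neither document states an order that would make the restriction harmless.

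The objections to the numbers stand in part. Both inputs are assumed, and at the low end the effect is negligible. The rates are for a simple t-test, not the SAP's ANCOVA, whose smaller residual variance could raise them. The figures at 200 per arm apply only if further funding arrives; a larger sample leaves the bias unchanged but makes a false rejection more likely.

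The missing-data and survey rules apply to both arms alike and do not show arm-specific selection. They matter here only because no statement that everyone is analysed as randomised stands beside them.

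**Conclusion.** The concern holds. As written, the protocol allows the two randomised arms to be selected by different rules, on a characteristic plausibly linked to the outcome, and neither document supplies a safeguard that closes the gap. Confidence is high about the wording and the missing time of randomisation. Whether any selection took place cannot be determined from the documents.

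If it did, the bias is p × δ, and its size rests wholly on those two assumed inputs. The illustrations range from negligible to a third of the effect the trial is sized for at 50 per arm, and two thirds of the smaller effect that the 200-per-arm maximum is meant to detect. The direction depends on whether refusers would have done worse or better than the rest. This should be fixed because it bears on the primary comparison and is cheap to resolve.

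**What to change.** **If enrolment is open.**
- Reword Protocol sections 4C and 11A so that pill willingness, mailing address and excipient allergy are asked of every candidate in the common prescreen of section 12D.
- State that randomisation follows confirmed eligibility and the second consent.
- Add a sentence to the SAP that everyone is analysed in the arm to which they were randomised.

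The cost is a wording amendment, a few items in the existing online prescreen and one SAP sentence. The downside is small: some otherwise eligible controls are screened out, and the trial population becomes people willing to take placebo pills.

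**If enrolment is complete**, as the SAP's past tense suggests.
- Report when these questions were asked and of whom.
- Report how many people were excluded after assignment, by arm.
- If any were, show how the primary result changes over a stated range of p × δ.

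The cost is a few lines of reporting and one sensitivity table. If everyone was asked before assignment, a sentence saying so settles the matter.
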